### 7.1.3 Targeted Physical Examination

A targeted physical examination will be limited to assessment of HEENT, chest, heart, abdomen and assessment of any site related to specific signs and symptoms reported by the subject.

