Administer study drug – reducing administration time and increasing study drug concentration in step-wise fashion at each visit per schedule 										X		X		X	

	Study Visit														
	Screening	Day 1 Baseline	Day 2	Day 4	Day 8 (1 wk)	Day 15 (2 wks)	Day 16	Day 18	Day 22 (3 wks)	Day 29 (4 wks)	Day 36 (5 wks)	Day 43 (6 wks)	Day 50 (7 wks)	Day 57 (8 wks)	Day 64 (9 wks)
Visit window (days)	(-28 days)	N/A	±3 hr	±3 hr	±1	±1	±3 hr	±3 hr	±1	±1	±1	±1	±1	±1	±1
Observe subject for 15 minutes post-administration; record vital sign measurements after completion of infusion and again at end of observation period 		X				X				X		X		X	

 All ART for the 3 months preceding Screening will be recorded at Screening visit; subsequent visits will only record changes to ART.

 Abbreviated physical examination includes examination of lymph nodes, respiratory and cardiovascular systems, abdomen, extremities, and nervous system.

 Only record AEs that are related to study procedures before administration of the first dose.

 Subjects do not need to fast before blood sampling.

 Serum FSH test to be conducted on postmenopausal females at Screening only.

 Pre-dose samples to be collected within 1 hour before the start of the infusion; 24 hr, 72 hr, and 7 Day post dose samples to be collected within 3 hours of the time the infusion ended.

 At Baseline and at Day 15 all subjects in the Sentinel Group (the first 5 subjects enrolled) will receive study drug diluted into 250 mL normal saline as a standard 800 mg IV infusion over 15 minutes, per Trogarzo® prescribing information. At Day 29, Sentinel Group subjects will begin receiving Trogarzo® 800 mg at increasing concentrations over decreasing intervals as follows: Day 29 (4 weeks) – 16 mg/mL delivered over 10 minutes (800 mg study drug diluted into 50 mL normal saline); Day 43 (6 weeks) – 50 mg/mL delivered over 5 minutes (800 mg study drug diluted into 16 mL normal saline); Day 57 (8 weeks) – 100 mg/mL delivered over 1 minute (800 mg study drug diluted into 8 mL normal saline). All subjects must be observed for 15 minutes after the completion of each study drug administration. Vital signs should be monitored and recorded at the beginning and end of the observation period.

 Any abnormalities observed need to be recorded on the AE CRF.

Schedule of Events – Sentinel Group (Subjects 1-5) (CONTINUED)

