### 7.1.2 Complete Physical Examination

A complete physical examination will include the following assessments: skin, head, eyes, ears, nose, throat (“HEENT”), chest including breasts and lungs, heart, abdomen, extremities and neurological exam. Height and weight will be measured at Screening and weight only at other times specified.

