### **3.4. Statistical Methods**

#### **3.4.1. General Overview and Plan of Analysis**

The data collected are intended primarily for clinical review and interpretation. The analysis of study data will be primarily descriptive, with emphasis on tabular and graphical displays. Descriptive statistics will be used to guide decisions as to the clinical relevance of findings. Unless otherwise stated, p-values will be determined only if they appear to be warranted from the summary statistics.

Where applicable, summaries will be displayed in the following subject groupings:

- IM HIV infected
- IM HIV uninfected
- Total

In addition, the safety and efficacy summaries will present results grouped by analysis periods, where applicable:

- IM HIV infected: Initial Period (15 min IV Infusion); Investigational Period (IM Injection); Follow-up Period (15 min IV Infusion)
- IM HIV uninfected: Pre-Steady State + IV Infusion Period; Investigational Period (IM Injection); Follow-up Period

For continuous data, descriptive statistics will be presented as number of subjects (n), mean, standard deviation, median, minimum, and maximum. For categorical data, the frequency and percentage of subjects in each category will be presented. Percentages will be based on non-missing data unless otherwise specified.

Data collected during this study will be assigned to the appropriate Analysis Phase, Analysis Period, and Analysis Sub period (where applicable) in which it occurred. The assignment will be based on the visit date, or in the case of cumulative data such as AEs and concomitant procedures, based on the start date. Tables, listings, and graphs will reflect the assignments. A complete description of the phases, periods, and sub periods for the HIV infected and HIV uninfected groups can be found in Appendix 1.

Data will be described and analyzed using the SAS System Version 9 (SAS Institute Inc., Cary, NC, SAS System). Individual subject data will be presented in subject data listings.

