#### **4.3.5. Physical Examination Findings**

A complete physical examination will be conducted at Screening and targeted physical exams will be conducted at every visit from Day 1 through Day 99 (14 weeks). Physical examination findings at each scheduled visit will be summarized overall for all subjects in the SAF Population. The number and percent of subjects with abnormal findings by body system will be tabulated.

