**Notes Applicable to All Tables**

General Programming Notes:

1. The tables will be programmed to show aggregate data only.
2. Review the data prior to programming. Check the data for inconsistencies and anomalies. Report suspected data errors to the lead programmer who can determine if they should be addressed by DM.
3. Follow the Quality Control Plans (\\\Westat.com\dfs\CTWRKGRP\PUBLIC\Resources\DA\QC\_Plans) for Tables, Listings, and Graphs. Perform the quality checks, using the Checklist.
4. Always check the population totals. All subjects should be accounted for in all tables. A row for "Unknown" or "Missing" values can be added to any table as appropriate to account for all subjects.
5. For summary statistics: N should always be an integer; minimum and maximum should have the same number of significant digits as is present in the data; mean and median should be calculated to be one additional significant digit than the data collected; standard deviation should be calculated to be two additional significant digits than the data collected.
6. Percentages should be calculated to one decimal place. The true number of treated subjects, which appears at the top of columns in most tables should be calculated once in libnames.sas and put into macro variables to ensure consistency. This number should not be re-calculated when calculating percentages.
7. Follow the mocks, especially regarding details, such as titles, capitalization, order of columns and row labels, and footnotes. Standard table formatting may be followed, as some mocks may have been created due to space/pagination considerations. The visit names in the mocks are examples only. Consult the protocol and SAP and present all scheduled visits for the item in question.
8. Additional footnotes may be required to fully/more accurately describe the contents of a table (decided during development). Consult project leader and lead biostatistician with questions.

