**Table 14.3.4.1**  
**Abnormal Physical Examination Findings**

**Safety Population**

		IM HIV Infected (N=XX)	IM HIV Uninfected (N=XX)	Total (N=XX)
Baseline [1]	Skin	n (xxx.x%)	n (xxx.x%)	n (xxx.x%)
	HEENT	n (xxx.x%)	n (xxx.x%)	n (xxx.x%)
	Lymph Nodes	n (xxx.x%)	n (xxx.x%)	n (xxx.x%)
	Lungs/Chest	n (xxx.x%)	n (xxx.x%)	n (xxx.x%)
	Heart	n (xxx.x%)	n (xxx.x%)	n (xxx.x%)
	Abdomen	n (xxx.x%)	n (xxx.x%)	n (xxx.x%)
	Genital/Rectal	n (xxx.x%)	n (xxx.x%)	n (xxx.x%)
	Extremities	n (xxx.x%)	n (xxx.x%)	n (xxx.x%)
	Neurological	n (xxx.x%)	n (xxx.x%)	n (xxx.x%)
Day 15	Skin	n (xxx.x%)	n (xxx.x%)	n (xxx.x%)
	HEENT	n (xxx.x%)	n (xxx.x%)	n (xxx.x%)
	Lymph Nodes	n (xxx.x%)	n (xxx.x%)	n (xxx.x%)
	Lungs/Chest	n (xxx.x%)	n (xxx.x%)	n (xxx.x%)
	Heart	n (xxx.x%)	n (xxx.x%)	n (xxx.x%)
	Abdomen	n (xxx.x%)	n (xxx.x%)	n (xxx.x%)
	Genital/Rectal	n (xxx.x%)	n (xxx.x%)	n (xxx.x%)
	Extremities	n (xxx.x%)	n (xxx.x%)	n (xxx.x%)
	Neurological	n (xxx.x%)	n (xxx.x%)	n (xxx.x%)
...				
End of Study [2]	Skin	n (xxx.x%)	n (xxx.x%)	n (xxx.x%)
	HEENT	n (xxx.x%)	n (xxx.x%)	n (xxx.x%)
	Lymph Nodes	n (xxx.x%)	n (xxx.x%)	n (xxx.x%)
	Lungs/Chest	n (xxx.x%)	n (xxx.x%)	n (xxx.x%)
	Heart	n (xxx.x%)	n (xxx.x%)	n (xxx.x%)
	Abdomen	n (xxx.x%)	n (xxx.x%)	n (xxx.x%)
	Genital/Rectal	n (xxx.x%)	n (xxx.x%)	n (xxx.x%)
	Extremities	n (xxx.x%)	n (xxx.x%)	n (xxx.x%)
	Neurological	n (xxx.x%)	n (xxx.x%)	n (xxx.x%)

N = All subjects in the Safety Population, and denominator for percentage calculations.

[1] Baseline is the last analyte value recorded, prior to the first dose administration.

[2] End of Study is Day 85 for subjects in the IM Group.

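### The physical-examination tables print nine body systems over the full Safety Population, but 3 to 5 of the nine are not routinely examined after Screening, so unexamined subjects are counted as not abnormal

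*Protocol*

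**What the plan says.** The complete examination, in Protocol 7.1.2, starts: "A complete physical examination will include the following assessments: skin, head, eyes, ears, nose, throat", and goes on to chest, heart, abdomen, extremities and neurological. It is done once. Section 4.3.5 of both SAPs (IM and IV push) says: "A complete physical examination will be conducted at Screening and targeted physical exams will be conducted at every visit from Day 1 through Day 99".

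The targeted examination has two definitions. Protocol 7.1.3 reads: "A targeted physical examination will be limited to assessment of HEENT, chest, heart, abdomen and assessment of any site related to specific signs" and symptoms the subject reports. Footnote 2, attached to the targeted-examination row in Tables 1 to 4, reads: "Abbreviated physical examination includes examination of lymph nodes, respiratory and cardiovascular systems, abdomen, extremities, and nervous system".

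For the analysis, section 4.3.5 of both SAPs says: "The number and percent of subjects with abnormal findings by body system will be tabulated". The shells are IM mock Tables 14.3.4.1 to 14.3.4.3 and IV push mock Tables 14.3.3.2.1 to 14.3.3.2.3. Each lists Skin, HEENT, Lymph Nodes, Lungs/Chest, Heart, Abdomen, Genital/Rectal, Extremities and Neurological at Baseline, Day 15 and on to End of Study. Each carries the footnote: "N = All subjects in the Safety Population, and denominator for percentage calculations". Programming note 6 for the tables adds, of the column N: "This number should not be re-calculated when calculating percentages". The general rule in section 3.4.1 of both SAPs is: "Percentages will be based on non-missing data unless otherwise specified".

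**The concern.** A percentage of subjects with an abnormal finding can be read as a rate only if the subjects in the denominator were looked at. Here the denominator is everyone treated, while the protocol does not call for several of the tabulated systems to be examined routinely after Screening. A blank then enters the table as a normal result.

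Two things are at stake. The first is the level: post-Screening rates for the affected rows are biased downward. The second is the comparison across periods. Where a Screening value stands in as Baseline, the Baseline cell comes from a systematic examination and the infusion, push or IM cells from a symptom-triggered one, so part of any decline would be a change in ascertainment. Skin is the row where this is least welcome. The protocol's own background reports rash at 13% as an adverse event in the Phase 2b trial, and skin disorders as the most frequent treatment-related class in the earlier SC/IM study (4 of 39, 10.3%).

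**Working it through.** The plan states no figure on this point, so there is nothing to reproduce. The check sets the nine table rows against the three lists. The mapping takes chest and respiratory as Lungs/Chest, cardiovascular as Heart, and nervous system as Neurological.

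| Table row | Complete (7.1.2, Screening) | Targeted, 7.1.3 | Targeted, footnote 2 |
|---|---|---|---|
| Skin | yes | no | no |
| HEENT | yes | yes | no |
| Lymph Nodes | no | no | yes |
| Lungs/Chest | yes | yes | yes |
| Heart | yes | yes | yes |
| Abdomen | yes | yes | yes |
| Genital/Rectal | no | no | no |
| Extremities | yes | no | yes |
| Neurological | yes | no | yes |
| Rows covered | 7 of 9 | 4 of 9 | 6 of 9 |

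Rows without routine examination after Screening: 9 − 4 = 5 under 7.1.3, and 9 − 6 = 3 under footnote 2.

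- Screening only under both definitions: Skin.
- Screening only under footnote 2: also HEENT.
- Screening only under 7.1.3: also Extremities and Neurological.
- In no list: Genital/Rectal. Lymph Nodes is in neither 7.1.2 nor 7.1.3.

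**Which denominator applies.** The non-missing rule in SAP 3.4.1 gives way where something else is specified. The shell footnote specifies the Safety Population, and note 6 forbids recalculating N. As written, the fixed N governs.

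**Illustration (assumed inputs).** Shown percentage = (abnormal subjects × share of them examined) / N, with N = 20, the planned IM Group. Suppose 4 subjects have an unchanged skin abnormality, so the true rate is 4/20 = 20%.

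- None examined later: 0/20 = 0.0%.
- A quarter examined: 1/20 = 5.0%.
- Half examined: 2/20 = 10.0%.
- All examined: 4/20 = 20.0%.

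For 2 to 6 abnormal subjects (10% to 30%), the later row shows 0% if none is examined, and 1/20 = 5% to 3/20 = 15% if half are.

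**The examined denominator has its own limit.** If 2 subjects are examined because of symptoms and 1 is abnormal, the fixed N gives 1/20 = 5% and the examined denominator gives 1/2 = 50%. The second is honest about who was seen but describes a selected subset, so it needs a label.

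**Whether the data allow it.** The mock physical-examination listings (IM 16.2.10, push 16.2.7.3) carry Not Done and Not Required statuses, so an examined count can be built. Their post-Screening rows follow footnote 2: six systems plus a line for additional findings. Skin and HEENT appear only in the Screening block of the push listing.

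**The case against.** The strongest reply is that little is lost. Under 7.1.3 a site with reported signs or symptoms is examined. Footnote 2 says what the examination includes without limiting it to that list, and the listings have a line for additional findings. A symptomatic rash can therefore reach the table. Under Protocol 8.2, subjects are also asked about adverse events at every visit and clinically significant physical findings feed adverse-event reporting. IM injection sites are assessed separately, and adverse events are tabulated by organ class, preferred term and period. The physical-examination tables support no test and no stopping rule. Programming note 4 also allows a Missing or Unknown row in any table. All of this stands and limits the harm, but it does not change the denominator that the shells specify.

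Several stronger readings are tempting and are not supported:

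- *The skin row must fall to 0%.* It need not. Asymptomatic, unreported findings are what is mainly lost.
- *HEENT is examined only at Screening.* That is so under footnote 2. Section 7.1.3 includes HEENT.
- *Every table compares a Screening-based Baseline with treatment.* IM Table 14.3.4.2 and the three push tables define Baseline as the last value recorded on Day 1, which is a targeted examination. The contrast arises only if the Screening value is carried in under SAP 3.3.4, and the SAPs do not say whether Not Required counts as missing.
- *About 13% of 20 subjects would have a rash shown as 0/20.* The 13% is adverse-event frequency over the Phase 2b trial, not prevalence at a visit. Nor is rash the most frequent event in the protocol's background: diarrhea is reported at 20% in the Phase 3 study.

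Finally, the push SAP cites a protocol dated 15 Oct 2020 whose examination text is not available here, so for the push tables the comparison rests on the current protocol.

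**Conclusion.** The tables are wrong as written, in the denominator. The targeted examination has two conflicting definitions. Under either one, 3 to 5 of the nine rows count subjects who were not routinely examined as not abnormal, and so tend to understate abnormality after Screening. Skin is affected under both definitions; Genital/Rectal is never examined. Where Screening values serve as Baseline, changes from Baseline in these rows partly reflect ascertainment.

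The size cannot be estimated: the documents give no visit-level prevalence and no indication of how often symptoms would trigger an examination, so the percentages above illustrate the mechanism only. The conclusion assumes that sites examine what the protocol lists and that programmers follow the shell footnote over the default in SAP 3.4.1. The effect is confined to descriptive safety tables. It does not mean that the trial would miss rash or injection-site reactions, which are captured by other routes.

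**What to change.** 1. Reconcile Protocol 7.1.3 with footnote 2 of Tables 1 to 4 so that there is one targeted-examination definition, preferably with a brief skin look at any visits still to come. Cost: one paragraph, four footnotes and a minute at an examination already scheduled. This cannot repair visits already completed.
2. In the six shells, show each system as number abnormal over number examined at that visit, using the Not Done and Not Required statuses. Replace the fixed-N footnote, exempt these tables from programming note 6, and footnote the systems examined only when symptomatic. State in SAP 3.3.4 whether Not Required is treated as missing when Baseline is set. Cost: shell and programming edits, no new data.
3. Remove the Genital/Rectal row. Keep the Skin row, with symptom-triggered findings shown as abnormal over examined. Dropping every row that is not routinely examined would delete the skin findings most worth seeing.

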### 7.1.4 Vital Sign Measurements

Vital sign measurements will include the subject’s heart rate (beats/minute), blood pressure (mm Hg), respiratory rate (breaths/minute), and oral temperature (°C). Measurements will be taken within 1 hour before the start of the study drug administration and again at both the beginning and end of the 15 minute (HIV-infected) or 60 minute (HIV-uninfected) post-administration observation period. Blood pressure and heart rate measurements will be obtained after the subject has been seated for at least 5 minutes. Ideally, each subject’s blood pressure should be measured using the same arm and the same size cuff at each visit.

### 7.1.5 Patient Reported Outcomes

Participants in the IM Group will be asked to complete questionnaires to assess their satisfaction with the different modes of Trogarzo® administration. The questionnaires will be administered at various visits (see Table 4). The Study Medication Satisfaction Questionnaire change version (SMSQc) is a self-reported assessment tool to assess the amount of change in treatment satisfaction

over time. The questionnaire was adapted from the HIV Treatment Satisfaction Questionnaire (HIVTSQ) to remove mentions of HIV and allow satisfaction evaluation in participants who do not have HIV (see [Appendix D](#)). HIV-infected participants in the IM Group will complete the HIVTSQ status version (HIVTSQs12) at Day 29 regarding IVI administration and at Day 85 regarding IM administration. In addition, they will also complete the change version of the questionnaire (HIVTSQc12) following completion of the IM portion of the study (Day 85). HIV-uninfected participants will complete the SMSQ status version (SMSQs) at Day 29 regarding IVI administration and at Day 85 regarding IM administration. In addition, they will also complete the change version of the questionnaire (SMSQc) following completion of the IM portion of the study (Day 85). Instructions and questionnaires are provided in Appendix D.

- HIV-infected IM Group Participants:
  - HIVTSQs12: questionnaire to be completed on D29 and D85
  - HIVTSQc12: questionnaire to be completed on D85
- HIV-Uninfected IM Group Participants:
  - SMSQs: questionnaire to be completed on D29 and D85
  - SMSQc: questionnaire to be completed on D85
- Preference assessment (Day 85): “For the past 8 weeks you have received IM injections every 2 weeks. Today we would like you to compare your experience on the IM injections with the IV infusion you received previously during this study. Which type of administration do you prefer?”.

## 7.2 Blood and Urine Samples

### 7.2.1 Clinical Laboratory Parameters

Collection of blood and urine samples for clinical laboratory assessments will be part of the safety profile assessment for the study subjects. Subjects do not need to fast before blood sampling. Samples will be processed using standard procedures as described in the laboratory procedures manual and will be analyzed by a central laboratory unless otherwise noted.

The samples will be analyzed for the following:

- **Hematology:** complete white blood cell count with differential, hemoglobin, hematocrit, and platelets. Prothrombin time and partial thromboplastin time will also be collected at Screening only for the IM group.

- **Serum chemistry profile:** albumin, alkaline phosphatase, ALT, amylase, AST, blood urea nitrogen, calcium, chloride, creatine phosphokinase, creatinine, direct bilirubin, gamma glutamyl transferase, glucose, lactate dehydrogenase, magnesium, phosphorus, potassium, sodium, total bilirubin, total protein, and uric acid.
- **Urinalysis:** visual inspection for appearance and dipstick assessment for color, pH, specific gravity, ketones, protein, glucose, bilirubin, nitrite, urobilinogen, and leukocyte esterase.

The urinalysis will be performed at the site by qualified personnel. If the results of the urinalysis are abnormal, a urine sample will be sent to the central laboratory for microscopic evaluation. Samples will be processed as described in the laboratory procedures manual before being sent to the central laboratory for evaluation.

Tests with Grade 3 or Grade 4 abnormal results should be repeated within 72 hours of the site becoming aware of the abnormal value(s) with the exception of CD4+ T cell levels. See [Appendix B](#) for details and definitions of toxicities. The investigator should discuss any Grade 3 or 4 abnormal laboratory results with the medical monitor/Sponsor for appropriate subject disposition, including potential withdrawal from the study. Refer to [Section 4.3](#) (Safety Monitoring and Toxicity Management Plan) for information on DMC reporting and subject discontinuation in the event of study drug-related AEs.

## 7.2.2 Archive Sample

A separate blood sample will be taken and stored for possible research use.

## 7.2.3 HIV-1 Viral Resistance Testing

Blood samples for HIV-1 viral resistance testing should be collected before the start of drug administration at the indicated visits in HIV-infected subjects only. Viral resistance testing will be conducted if a subject experiences an increase in plasma viral load to levels above 1,000 copies/mL on 2 consecutive measurements at least 2 weeks apart. Resistance testing will include assessments of reverse transcriptase, protease, integrase, and envelope genes and chemokine coreceptor utilization; the samples will be collected and stored.

## 7.2.4 HIV-1 RNA Level

Blood samples for viral load will be collected at Screening, Day 1, and at several additional timepoints through the study and used to determine study qualification as well as the effectiveness of the study regimens and should be drawn before drug administration in HIV-1 infected subjects only.

